The underlying principle of co-production and methodology of PAR are critical to our Research approach as they necessitate: working directly with persons affected, policy makers and programme implementers to define the problem, generate and evaluate solutions to facilitate rapid uptake of best practices; and utilising accessible and adaptable communication techniques to ensure that findings are packaged and disseminated to target audiences through a two-way process of dialogue and exchange. Additionally, specific attention will be given to the inclusivity in accessibility of programme outputs, with, for example, easy read versions of outputs being produced. We are working in direct collaboration with the Ministry of Health, Ghana Health Services and persons affected whose needs this research responds to.

Four core and two cross-cutting work packages (WP) will synergistically enable co-production, measurement, implementation and evaluation of interventions to drive forward integrated management of NTDs and MHCs.

A mixed methods approach will be used to achieve the five objectives through the four study phases.

Phase 1: Design phase

In order to respond to workpackage 1, we will seek to document the readiness of the health system to facilitate integrated implementation of interventions for NTDs and MHCs and to catalyse collaborative action amongst regional, national and sub-national stakeholders, including persons affected. This rapid context analysis will take three main approaches:

- 1) A health systems readiness survey will involve the collation a series of key indicators at health facility level, which will be collated based upon review of existing ledgers and data within the facility, as well

as qualitative responses with health workers (the qualitative questions are integrated within existing qualitative tools). The purpose of this tool is to understand the readiness of the health system across levels at hospital, health centre and clinic level to integrate mental health and stigma reduction activities as part of the Essential Care Package for patients with skin NTDs.

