District/ DHMS (5 participants*4 districts) Data manager Disease control officer District MH nurse District PH nurse District director of health services	KII	Who are the types of health workers currently managing and delivering NTD and mental health services at all health system levels? What are the views of health providers on the advantages and disadvantages, opportunities and constraints of integrated service delivery for NTDs and MHCs?
Facility level (3 facilities*4 districts) One hospital, one health centre and one clinic per district	Health systems readiness assessment	What is the readiness of the health system to integrate mental health within care for people with NTDs?

Participant	Method	Research question
Health facility (3 facilities*4 districts*6 participants) One hospital, one health centre and one clinic per district Disease control officer (some facilities only) MH nurse PH nurse In charge (facility manager) OPD clinician Adolescent corner	IDI	Who are the types of health workers currently managing and delivering NTD and mental health services at all health system levels? What are the views of health providers on the advantages and disadvantages, opportunities and constraints of integrated service delivery for NTDs and MHCs?
Community level (IDI*2CHW per facility*3 facilities*4 districts) CHWs	IDI	
Community level (1FGD*3 facilities*4 districts) Community health volunteers/ Community drug distributors	FGD	
Community level (3 FGDs*4 districts*6 participants) Leprosy group, Student club for NTD Other NGOs working with MH or NTDs Male group, female group, adolescent group	Asset mapping FGD	Asset mapping to explore what is happening already
Community level (2 participants*4 districts) Community leaders	Asset mapping IDI	
Pluralistic provider (3*4 districts*6 participants) Traditional Healer Herbalist Faith healer	IDI with vignette	What are the existing and potential roles of pluralistic providers (e.g. religious leaders, traditional healers) in the delivery of interventions for NTDs and/or MHCs?
Persons affected and caregivers (2 groups* 4 districts*2) 1 male FGD, 1 female FGD	FGD followed by Photovoice	What do people affected believe are the priority interventions and strategies that could improve their mental wellbeing?

Participant	Method	Research question
NTDs and MHC		
Persons affected (1 group* 4 districts) NTDs and MHC	Problem tree Matrix ranking	

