Narrative Case Study Interviews (20 case studies (5 per district) Person affected leprosy + caregiver Person affected BU + caregiver Person affected LF + caregiver Person affected by cutaneous leishmaniasis + caregiver Person affected by onchocerciasis + caregiver	Narrative Case Study Interviews	What are the syndemic relationships between NTDs, mental health conditions and disability? How applicable are existing intervention approaches from other settings relevant to addressing these interactions in Ghana?

3) Policy analysis of existing programme documents to understand the necessary tools and resources required to facilitate integrated implementation, as well as the current policy context within Ghana relating to NTDs and mental health.

The primary purpose of the policy analysis will be to develop an understanding of the policy processes, stakeholders and structures that may impact the development and delivery of the integration of mental health within care for people with NTDs in Ghana. This will inform the research design as well as the way that evidence is synthesised, packaged and disseminated. The policy analysis will primarily focus on national policy.

Documents will be obtained by liaising with stakeholders in the Ministry of Health and Ghana Health Service. Once documents are obtained, we will develop a thematic framework to rapidly extract data from the documents, before synthesising the data from all the reports.

Baseline survey with persons affected and general population

At this stage, a census approach will be used to survey all persons affected by NTDs in our study sites. The purpose of this survey is to establish the prevalence of mental health conditions amongst persons affected and examine factors associated with reduced mental health/wellbeing; and gather data that will serve as the baseline for our impact evaluation. The survey will consist of tools recommended in the NTD morbidity toolkit, including the PHQ-9, GAD-7, Warwick mental wellbeing scale, to capture our main study outcomes, namely depression, anxiety and wellbeing. We will also use the EQ-5L-5L

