Baseline survey: We will conduct use a census approach to survey the NTD population in the 4 intervention sites (expected n=200). NTD patients will be identified as follows: We will work with the district health directorate to identify health facilities with NTD cases in each intervention district (CHPS and health centres). Where available, we will obtain a list from the district health officer with names and contact numbers of persons affected with NTDs registered in these facilities. We will also visit traditional/faith healers in the vicinity of the selected health facility, to ask if they have any NTD patients under their care. Finally, we will speak to community health workers

attached to the local facility, and, upon completion of the survey, we will ask persons affected if they know of anyone else who is affected by one of the target conditions, to identify any non-registered persons affected via snowballing method. As such, it is expected that our census will contribute to case finding. The number of target health facilities will be expanded until we reach the required sample size; once a health facility is selected, we will complete our census, even if this takes us beyond the required sample size.

The first approach will be made by a research assistant, together with a CHV, who will visit the person affected in the community. The research assistant will verbally explain the purpose of the study and provide an information sheet. If the participant is happy to participate, the research assistant will agree to return the next day, or at a date and time of the participants choosing. On the day of the survey, the research assistant will again explain the purpose of the study, provide an opportunity to ask questions and obtain written informed consent via thumbprint or signature.

Policy brief

The primary purpose of the policy analysis will be to develop an understanding of the policy processes, stakeholders and structures that may impact the development and delivery of the integration of mental health within care for people with NTDs in Ghana. This will inform the research design as well as the way that evidence is synthesised, packaged and disseminated. The policy analysis will primarily focus on national policy.

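### The baseline survey is called a census of all persons affected, but its register lists come only from CHPS and health centres, so persons registered only at hospital have no register route in

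*Protocol*

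**What the plan says.** **Target population.** In the Protocol, Phase 1, under Baseline survey with persons affected and general population: "a census approach will be used to survey all persons affected by NTDs in our study sites". The survey is to establish the prevalence of mental health conditions and to serve as the baseline for the impact evaluation.

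**Frame.** In the Protocol, Recruitment and sampling, Baseline survey paragraph, the aim is to "survey the NTD population in the 4 intervention sites (expected n=200"). The team will work with the district health directorate to "identify health facilities with NTD cases in each intervention district (CHPS and health centres"), and will then obtain, where available, a list with "names and contact numbers of persons affected with NTDs registered in these facilities".

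**Other routes, same paragraph.** "We will also visit traditional/faith healers in the vicinity of the selected health facility". "Finally, we will speak to community health workers", namely those attached to the local facility. Respondents are also asked, after the survey, whether they know anyone else affected, as a way to find persons who are not registered. Facilities are added until the required sample size is reached.

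**Hospitals elsewhere.** Phase 1 describes the health systems readiness survey as a means to understand the "readiness of the health system across levels at hospital, health centre and clinic level to integrate mental health and stigma reduction activities" within the Essential Care Package. Table 2 specifies "One hospital, one health centre and one clinic per district" for both the readiness assessment and the health worker interviews, so four hospitals across the four districts.

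**The concern.** The population that the survey claims to cover is wider than the frame used to find it. The hospital is a study level for facility assessment and staff interviews, but not for finding the patients who are surveyed, and the protocol gives no reason for the difference.

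The survey has two uses. It supplies the prevalence of depression and anxiety, and it is the first measurement of the cohort that Phase 3 follows to 12 months. A person missed at baseline therefore has no baseline value later. The Quantitative data section also plans regressions of mental health on symptom severity, disability and functioning. If level of care follows severity, which is plausible but not documented, the frame selects on a variable that the analysis means to study. A larger sample from the same frame does not remove a coverage error.

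**Working it through.** The plan has no figure to reproduce. The expected 200 comes with no precision target, power or effect size, and this point does not dispute it.

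**Step 1: set the texts side by side.**

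| Element | Protocol text | Hospital included? |
|---|---|---|
| Target population | All persons affected in the study sites | Yes, by implication |
| Register lists | CHPS and health centres | No |
| Healer visits | Near the selected facility | Indirectly |
| Community health workers | Attached to the local facility | Indirectly |
| Snowballing | Starts from persons already surveyed | Indirectly |
| Readiness survey, staff interviews | One hospital per district | Yes |

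The target and the frame do not match. The three supplementary routes can reach a hospital-registered resident, but each starts from a selected lower-level facility or from someone already found. Adding facilities under the expansion rule, as worded, adds more of the same types. That brings more healers, workers and snowball chains, but no register listing hospital-only patients.

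**Step 2: illustrate the possible size.** All inputs except n are assumptions, because the documents give none of them.

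- h = share of eligible persons registered only at hospital: 5% to 30%
- c = share of those found by the other routes: 0% to 80%
- d = difference in depression prevalence between hospital-only persons and the rest: 10 to 30 points, in either direction
- n = 200 (Protocol, expected size)

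All other eligible persons are taken as found.

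Missed per 200 eligible = 200 × h × (1 − c).

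- Low: 200 × 0.05 × 0.20 = 2
- High: 200 × 0.30 × 1 = 60

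Share of hospital-only persons among those found = hc / [1 − h(1 − c)].

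Absolute bias in prevalence = {h − hc / [1 − h(1 − c)]} × d.

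- Low (h = 0.05, c = 0.8, d = 10): 0.05 − 0.04/0.99 = 0.0096; × 10 = 0.1 points
- Middle (h = 0.20, c = 0.5, d = 20): 0.20 − 0.10/0.90 = 0.0889; × 20 = 1.8 points
- High (h = 0.30, c = 0, d = 30): 0.30 × 30 = 9.0 points

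**Step 3: scale.** 95% half-width = 1.96 × √[p(1 − p)/200].

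- p = 0.2: 1.96 × 0.0283 = 5.5 points
- p = 0.5: 1.96 × 0.0354 = 6.9 points

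These half-widths assume simple random sampling and serve only as a yardstick. The middle case lies well inside them and the extreme case exceeds them.

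**The case against.** The best defence is that registers are only one of four routes. Healer visits, community health worker enquiries and snowballing are deliberate steps. Workers and neighbours know residents by their condition, not by where they are registered. Snowballing is described as aimed at non-registered persons, but the question put to respondents is about anyone else affected, so it can also bring in hospital patients. Each added facility extends these routes. This stands: a reader might infer that hospital patients are missed unless found by chance, and the text does not support that. What remains is that none of these routes is a systematic one to hospital patients, and their yield is unknown.

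A reader might also infer that the package will be delivered at hospitals and that the survey therefore leaves out part of the intervention population. The protocol commits only to assessing readiness at hospital level. The intervention is still to be designed, and evaluation details are deferred to an amendment. Hospital delivery is a reasonable inference but not a stated decision.

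A third tempting reading is that the severe end is cut off and prevalence is understated. Nothing in the documents says that anyone is registered only at hospital, or that such patients are more severely affected or more depressed. Nor does a narrower range of severity by itself bias the slope of a correctly specified linear model; it costs precision. And persons on a CHPS or health centre list may also attend hospital, so it does not follow that the cohort will lack hospital users.

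None of this reconciles a census of all persons affected with a register frame that names two facility types.

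**Conclusion.** The point holds as a mismatch between the stated target population and the sampling frame. Persons registered only at hospital have no register route into the survey, and adding CHPS or health centres does not create one. The documents fix neither their number nor the direction or size of any bias. On the stated assumptions the error in prevalence runs from about 0.1 to 9 points, with 1.8 points in a middle case, so it may be negligible or may exceed sampling error. The case for change rests on the mismatch and on the low cost of removing it, not on a demonstrated bias. If the bracketed facility types were meant only as examples, the same edit removes the ambiguity.

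**What to change.** In the Baseline survey paragraph of Recruitment and sampling:

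1. Add the district or municipal hospital's NTD register, where one is available, as a list source in each of the four sites.
2. Restrict that list to residents of the catchments of the selected CHPS and health centres. If the whole hospital list were used while only a fraction f of lower-level patients enter through selected facilities, the hospital-only share of the combined register lists would be h / [h + f(1 − h)]. This exceeds h whenever f < 1, so one distortion would replace another.
3. Remove duplicates against the lower-level lists.
4. Record each respondent's level of registration and the route by which they were found, so that the yield of each route can be reported.

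If hospital registers are not to be used, narrow the target population in the Phase 1 survey section to persons reachable through the selected CHPS and health centres and the community routes around them, and report prevalence for that population.

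The cost is one extra list per site, de-duplication and some catchment matching, which depends on usable residence data in the hospital register. The readiness survey already reviews ledgers at one hospital per district, so no new type of site is needed.

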This phase will involve a multi-disciplinary evaluation of the intervention bundle to make recommendations for future delivery of an essential care package for co-occurring NTDs and MHCs. The details of the evaluate phase will be determined following development of the intervention, and so the methods included in table 2 are provisional for now, and may be adjusted and updated in the amendment to be submitted once details on the intervention are known. Participant numbers for these methods have not yet been estimated and will be included in the subsequent amendment.

Our evaluation takes a realist theory-based approach and is concerned with understanding; what components of our intervention bundle are effective, with which implementation strategies, for whom, in what settings and for how long (Holtrop et al, 2021). We are focused on understanding the impact of the different dimensions of our intervention bundle and the contexts in which they are and

are not effective. Our multi-disciplinary evaluation will be guided by the RE-AIM framework (Holtrop et al, 2021). The RE-AIM framework consists of five core domains that are designed to be considered at different implementation levels from the perspective of different stakeholders: **Reach** and **Effectiveness** (Individual level); **Adoption** and **Implementation** (facility, system and policy level); and **Maintenance** (all levels) (Holtrop et al, 2021).

A range of qualitative methods will be used to evaluate the intervention alongside the quantitative aspects.

The quantitative aspect of the evaluation will consist of a longitudinal cohort study with repeated measures at baseline and 12 months after the start of intervention, to track individual level changes and do an initial assessment of sustainability of the intervention. We will track engagement with the intervention via an 'intervention passport', in which persons affected will collect stamps/stickers for every engagement with the health system in relation to their NTD/Mental Health condition. The evaluation will also include a cost-consequence and cost-effectiveness analysis.

Phase 4: Adjust phase

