This phase will work with all stakeholders to review and adapt interventions and to embed successful components within the routine health system management of co-occurring NTDs and MHCs and to make recommendations for the scale-up of the essential care package within Ghana and across the West African region, which may take the form of participation of West African MOH during final dissemination workshop with linked learning visit.

Overview of Methods

Key informant interviews

National and district level KIIs will be conducted with different stakeholders to understand the current situation within Ghana regarding existing strategies for the integrated management of co-occurring NTDs and mental health conditions from the perspective of national stakeholders. Envisaged national and district-level stakeholders to be interviewed are listed in Table 3.

Key informants will be purposively selected, according to their knowledge and experience linked to their job role and knowledge of NTD programme, health systems service delivery including human resource management, and broader health and wellbeing in Ghana. The country research teams will approach the key informants through a letter and a follow up telephone call. The purpose of the interview will be made clear to each participant, and they will be asked to provide informed consent and, where relevant, consent of the organisation that they are representing.

Table 3. KII sampling frame and research questions

Participant	Research question
National level participants MOH – MH dept GHS – MH unit GHS - data manager	Who are the types of health workers currently managing and delivering NTD and mental health services at all health system levels? What are the governance structures and policies of the health system that are currently helping

NTD programme (covers LF, Oncho) BU/yaws programme director Leprosy programme director Public health Director	and hindering collaboration and co-ordination between NTD and mental health service providers? (e.g. policies on organisational interactions and communications between ministerial departments; review of NTD masterplans and associated targets etc). What are the current budgeting processes, financing mechanisms, and resources available to support the delivery of interventions for NTDs and MHCs?

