At baseline, we will first use the NTD population dataset, to explore our main outcomes (mental health and quality of life of people affected). Using descriptive statistics, we will calculate the prevalence of depression and anxiety and summarise other key variables. The data will be presented separately by sex. We will use inferential statistics (multivariable linear regression analysis) to explore associations between mental health, quality of life, stigma and demographic variables. We will include interaction effects to see if the effect of predictors on our main outcomes differs from sex.

We will also specifically explore the relationship between mental health and time since diagnosis, symptom severity, disability and functioning, using inferential statistics (multivariable linear regression), including interaction terms between key variables and sex.

The endline analysis will include descriptive statistics to summarise outcomes at each time point, stratified by sex. To evaluate changes over time and potential sex differences, we will use linear mixed-effects models with random intercepts for participants. Fixed effects will include time, sex, and a time \times sex interaction term to assess whether the trajectory of mental health outcomes differs between males and females. Model assumptions will be checked, and sensitivity analyses will be conducted as appropriate.

Findings from both qualitative and quantitative analyses will be integrated to provide a holistic understanding of how mental health services can be effectively incorporated into NTD programs. Triangulation of data sources will enhance the reliability and validity of study findings, ensuring that recommendations are evidence-based and actionable.

Dissemination, Outputs and Anticipated Impact

Our approach to impact is guided by our IMAGINE Ghana Theory of Change (Figure1); and which will be regularly reviewed at consortium meetings to reflect any changes in context.

[figure not shown]

Figure 1. Overview of IMAGINE Ghana study phases and work packages

Our impact at the **global level** will be to: Drive advances in the **development and evaluation of interventions and strategies for improved treatment and management of co-occurring NTDs and MHCs within LMICs**.

Our global impact will be accompanied by impact within Ghana at three key levels:

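### The stated models have no level above the participant although recruitment takes in whole facilities, so some standard errors can be too small

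*Protocol*

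**What the plan says.** **Sampling** (Protocol, Recruitment and sampling, Baseline survey). About 200 people are expected across the four sites. The facility is the working unit of recruitment: "The number of target health facilities will be expanded until we reach the required sample size", and "once a health facility is selected, we will complete our census, even if this takes us beyond the required sample size". People under the care of nearby healers and people known to attached health workers are added. Participants are then asked about others, "to identify any non-registered persons affected via snowballing method".

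**Analysis** (Protocol, Data Analysis, Quantitative data). At baseline: "We will use inferential statistics (multivariable linear regression analysis) to explore associations between mental health, quality of life, stigma and demographic variables". At endline: "we will use linear mixed-effects models with random intercepts for participants", with time, sex and their interaction as fixed effects. Facility and district appear in neither model, and no cluster-robust variance is mentioned. Checks of assumptions and unspecified sensitivity analyses are allowed for, but clustering is not among anything named.

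**Purpose.** Phase 3 (Evaluate phase) asks "what components of our intervention bundle are effective, with which implementation strategies, for whom, in what settings and for how long", using two measurement waves. Phase 4 (Adjust phase) is to "make recommendations for the scale-up of the essential care package within Ghana and across the West African region".

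**The concern.** People who attend the same facility, live in its catchment or refer one another are likely to resemble each other in disease, access to care and stigma. A model that treats them as independent credits the data with more information than they hold. This is not only a gap that an SAP might fill: the Protocol writes out the fixed and random parts of its models, and they do not match the sampling it describes.

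The conclusions are meant to support scale-up beyond the facilities enumerated, so variation between facilities belongs in the stated uncertainty. If it is left out, baseline associations may look firmer than they are. So may the overall change after the intervention, if the package works better in some facilities than in others.

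**Working it through.** **Inputs.** From the Protocol: n = 200 expected, two waves, and the models above. The 200 cannot be reproduced because no derivation is given. Not in the Protocol, and therefore assumed: the number of survey facilities k (12, 24 or 40, equal sizes unless stated) and the ICC (0.01 to 0.10). The 3 × 4 = 12 facilities in Table 2 belong to the readiness assessment, so 12 is only one illustrative value.

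**1. Baseline mean or prevalence.** Design effect DEFF = 1 + (m − 1) × ICC, with m = 200/k. For k = 12 and ICC 0.05: 1 + (16.67 − 1) × 0.05 = 1.78, and effective n = 200/1.78 = 112. A 95% half-width at 50% prevalence is 1.96 × √(0.25/200) = 6.9 points without clustering, and 6.93 × √1.78 = 9.3 points with it.

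| k | m | DEFF, ICC 0.01 | DEFF, ICC 0.05 | DEFF, ICC 0.10 | Effective n, ICC 0.05 | Half-width at 50%, ICC 0.05 |
|---|---|---|---|---|---|---|
| 12 | 16.7 | 1.16 | 1.78 | 2.57 | 112 | 9.3 |
| 24 | 8.3 | 1.07 | 1.37 | 1.73 | 146 | 8.1 |
| 40 | 5.0 | 1.04 | 1.20 | 1.40 | 167 | 7.6 |

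**2. Baseline predictors.** Actual coverage of a nominal 95% interval is 2Φ(1.96/√DEFF) − 1. Results are for k = 12 / 24 / 40 and an outcome ICC of 0.05.
- Predictor constant within facility: 86% / 91% / 93%. Simulation (4,000 runs) gives 85.6 / 90.8 / 92.7.
- Predictor with its own ICC of 0.3: DEFF ≈ 1 + (m − 1) × 0.05 × 0.3 = 1.24 / 1.11 / 1.06, so 92% / 94% / 94%. Simulation agrees (92.0 / 93.8 / 94.4).
- Sex, balanced within facilities: about 95% (simulation 94.5 to 95.4).

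With an outcome ICC of 0.01, even the facility-constant predictor is at about 93% / 94% / 95%.

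**3. Change from baseline to 12 months.** Write an outcome as facility level + person level + time × (average change + facility deviation in change) + error. In the within-person difference the facility level and the person level cancel, and only the facility deviation in change remains. The variance of the mean change is therefore inflated by 1 + (m − 1) × (ICC of change), and by nothing if that ICC is zero. With complete pairs the participant-intercept model estimates the average change by the mean paired difference. Simulated coverage for k = 12 / 24 / 40:
- facilities differ in level only (ICC 0.05): 94.9 / 94.8 / 94.9%;
- ICC of change 0.05: 85.8 / 91.4 / 92.7%;
- the same with unequal facility sizes: 81.9 / 87.9 / 91.6%;
- time by sex, across scenarios: 93.9 to 95.3%.

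A separate simulation of 20,000 data sets (12, 20 and 40 facilities) gave true-to-model SE ratios for the mean change of 1.01, 0.99 and 1.00 without facility differences in change, and 1.34, 1.21 and 1.09 with them. For time by sex the ratios were 0.99 to 1.00. Fitting the mixed model itself with 20% dropout and 12 facilities gave 1.02 and 1.28 for time. Time by sex was 0.99 and 1.13 there, but with only 150 data sets a ratio carries an error of about 1/√300 = 6%.

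**4. Which remedies work.** In one fitted data set with 24 facilities and facility differences in change, the SE of time was 0.0683 with the participant intercept, 0.0683 after adding a facility intercept, 0.0839 with a facility slope for time, and 0.0837 with facility-clustered errors. With few clusters the correction matters: for a facility-constant predictor and 12 facilities, ordinary clustered errors (CR1, k − 1 df) cover 88.9%, and CR2 with Satterthwaite df covers 96.1%.

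**The case against.** - **Room for the SAP.** The Protocol names model families and does not forbid clustered errors, it allows sensitivity analyses, and it calls the Phase 3 methods provisional. This lowers the stakes at endline. It does not cover the baseline regression, and a general allowance for sensitivity analyses does not put facility into either stated model.
- **Census.** If everyone affected in the four sites were enumerated, descriptive figures for them would carry no sampling error. That stands for purely descriptive figures. But facilities are added only until a target size is reached, inferential models are used, and recommendations reach further than the sites.
- **The largest figures attach to analyses that are not stated.** Prevalence is to be descriptive with no interval mentioned, and the named predictors are measured on individuals. This stands in large part. For a predictor with moderate clustering the loss is 1 to 3 points of coverage, and disease type, the likeliest strongly clustered variable, is collected but not named as a predictor.
- **Change.** That change varies by facility is not shown. This is true; the Phase 3 question about settings only makes it plausible.
- **Purposive sites.** Clustered errors would not by themselves justify inference to Ghana or West Africa. That is correct; they remove one source of overstatement only.
- **Identifier.** Nothing says that facility will go unrecorded, and the search is organised by facility. The request is a precaution.

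**Conclusion.** The concern holds, with modest stakes. The written models omit the level at which people are recruited. Standard errors are too small for baseline means (where an interval is reported) and for predictors that cluster by facility, if outcomes correlate within facility. They are too small for the average change only if change differs between facilities. Sex and time by sex are essentially unaffected.

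The size cannot be settled from the Protocol. Over 12 to 40 equal facilities and ICCs of 0.01 to 0.10, standard errors should be larger by a factor of √1.04 = 1.02 to √2.57 = 1.60. With many small facilities and a low ICC this is negligible; with about a dozen facilities and an ICC of 0.05 or more it could change the reading of a result. The baseline work is exploratory and no primary test is named, so this is an improvement worth making and not a flaw that invalidates the study.

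**What to change.** **At the baseline survey.** Record the facility or catchment for every participant. Fix a simple rule for people found through healers or snowballing, for example the selected facility whose enumeration led to them. This is the time-critical part, because such links are hard to reconstruct later.

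**Baseline analysis.** Use facility-clustered standard errors with a small-sample correction (CR2 with Satterthwaite df) or a facility random intercept, with district as a fixed effect. Use design-based intervals for any prevalence reported with an interval.

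**Endline analysis.** Use facility-clustered standard errors with the same correction, or a facility random slope for time if it can be estimated. A facility intercept or a district main effect alone does not correct the time effect.

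**Cost.** One data field, one allocation rule and a different variance estimator in R. The endline part can go into the amendment that Phase 3 already announces. The price is wider intervals and few degrees of freedom (Satterthwaite df of about 4 for a facility-level predictor with 12 facilities). A random slope may not be estimable from two waves, in which case the clustered errors should be used.
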